9.7 Interim Analysis

No interim statistical analysis is planned during this study. However, ORR will be evaluated throughout the study as per the Bayesian Predictive Probability Design in order to decide whether or not a group should be stopped for lack of tumor response.

9.8 Internal Data Management Committee

Interim data will be reviewed for the purpose of study expansion decision making. The Internal Data Monitoring Committee (IDMC) will be comprised of a limited group of Sponsor representatives not directly involved in the conduct of the study. The IDMC will review emerging data in accordance with a separate charter. Investigators will be informed of enrollment decisions but details of efficacy results will be protected until communication points specified in the IDMC charter.

9.9 Evaluation of Enrollment Stopping Rules

Disease response and progression as documented by the investigator in the CRF will be the basis for evaluation of the enrollment stopping rules. The following guidelines will apply to each treatment arm when determining number of events in the numerator and denominator in the stopping rules:

1. The numerator will include patients with objective responses (PR or CR) at any time prior to disease progression as assessed by the investigator and documented in the CRF. Unconfirmed responses will be included until sufficient time has elapsed to allow confirmation of response; if the response is not confirmed, the response will be excluded from the numerator during subsequent reviews.
2. The denominator will include:
 - a. Patients included in the numerator;
 - b. Patients discontinued from treatment;
 - c. Patients at the second or subsequent on-study disease assessment (scheduled after 4 treatment cycles, at Week 13) without PR, CR or PD (i.e., patient has Stable Disease [SD] or Not Evaluable [NE]).
3. The denominator will exclude:
 - a. Patients on treatment that have not yet reached the first on-study disease assessment;
 - b. Patients on treatment with SD or NE at the first on-study disease assessment (scheduled after 2 treatment cycles, at Week 7).

At each evaluation of stopping rules, the contribution of each participant's experience to the numerator or denominator will be updated based on current data. For example, a patient having SD at Week 13 may contribute only to the denominator at one evaluation, but be included also in the numerator at the next evaluation based on new data documenting PR or CR at Week 19.

A degree of discordance is expected between investigator assessments of disease response/progression and central review of disease response/progression. No attempt will be made to retrospectively apply the later emerging central review assessments to the enrollment stopping rules.

The IDMC may elect to apply the Bayesian Predictive Probability Design only to those patients taking the SDD formulation in order to mitigate the potential confounding effects from formulation change. These details are outlined in the IDMC charter.

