Using the parameters identified, the ultimate sample size for each treatment arm is as many as 45 patients in the mITT population. The stopping rules (rejection regions), expressed as number of responses per patients treated, are 0/10, 1/14, 2/18, 3/22, 4/26, 5/29, 6/32, 7/35, 8/37, 9/39, 10/41, 11/43, 12/44, and 13/45. Thus, if more than 13 responses are observed among the first 45 patients enrolled who meet the criteria for the mITT population, the drug will be declared efficacious. If the true ORR is 20% (null hypothesis), the probability of early termination during the study is 0.92, and the expected sample size prior to termination is 28 patients; the Type 1 error equal to 0.0499 and Power equal to 0.9065. If the true ORR is 40% and $N=45$, the exact 95% confidence interval (Clopper-Pearson) around the point estimate for ORR will be (25.7; 55.7).

If the outcome is promising and the option is taken to enroll an additional number of patients up to 100 in the mITT population in a specific treatment arm to increase the size of the safety database and narrow the confidence interval around the ORR point estimate, the 95% confidence interval around a true ORR of 40% will be (30.3; 50.3). Data collected in patients enrolled beyond the planned Phase 2 sample size will be used in secondary and supportive analyses.

For the purpose of making decisions for continued enrollment and for conduct of the final analysis for the Phase 2, the mITT population is defined as all patients who receive at least one dose of MGCD265.

Table 1: Pre-screening Assessments

To establish potential eligibility for future enrollment into Study 265-109, pre-screening for tumor genotype may be performed in advance of anticipated clinical screening for study entry, e.g., during treatment with chemotherapy required prior to study entry.

	Guidance
Informed Consent for Tumor Genotyping Pre-screening	Informed consent must be obtained prior to sending tumor tissue or blood for Sponsor-approved local or central laboratory genotyping. The informed consent form and process may be performed in accordance with documented institutional practice or using the study-specific, IRB-approved pre-screening ICF. An IRB/EC approved process for obtaining consent from patients who are remotely located may be used.

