3 STUDY DESIGN

Study 265-109 is an open-label, parallel arm, Phase 2 trial evaluating the tumor response to MGCD265 in patients with locally advanced, unresectable or metastatic NSCLC exhibiting activating genetic alterations of *MET*.

To be eligible for enrollment, patients must have documented evidence of a genetic alteration activating *MET*, based on molecular testing performed by a Sponsor-approved central or local laboratory.

The primary objective of the study is to determine the tumor response with MGCD265 as measured by ORR in accordance with RECIST 1.1. Secondary objectives include evaluation of safety, secondary efficacy endpoints, tumor genetic alterations in tumor tissue and ctDNA at prescreening/baseline, change in ctDNA through time, and population PK/PD. Schedule of Assessments to be performed in the study is presented in Table 1, Table 2, and Table 3.

MGCD265 will be administered as an oral therapeutic twice daily (BID) in 21-day cycles. Guidelines for study drug administration and dose reduction in the event of toxicity are provided in Section 5.2. Study treatment will continue until disease progression, unacceptable adverse events, patient refusal or death.

Disease response and progression as documented by the investigator in the CRF will be the basis for patient management, study expansion decision making, and secondary and supportive statistical analyses. Central radiology review for disease response will be the basis for the primary statistical analyses to estimate the objective response rate and its confidence interval as well as the duration of response and PFS. The importance of timely and complete disease assessments in this study is critical for the efficacy endpoints. The need to truncate treatment cycles to manage toxicity may result in inconvenient scheduling of disease assessments. Disease assessments must be performed as scheduled according to the calendar to prevent the introduction of bias into the assessment of efficacy based on toxicity.

This Phase 2 parallel-arm study will be conducted in four groups of patients having genetic tumor alterations activating *MET*:

- A. *MET* activating mutations in tumor tissue,
- B. *MET* gene amplifications in tumor tissue,
- C. *MET* activating mutations in ctDNA, and
- D. *MET* gene amplifications in ctDNA

Full and timely enrollment of patients into Treatment Arms A and B are central to this study meeting its objectives. In addition, for patients enrolled based on a

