6.5 Patient Discontinuation/Withdrawal

Patients may discontinue from study treatment or from the study at any time at their own request, or they may be discontinued at any time at the discretion of the investigator or Sponsor for safety, behavioral reasons, or the inability of the patient to comply with the protocol required schedule of study visits or procedures at a given study site.

Criteria that may be used to discontinue patients from receipt of study medication will include, but will not be limited to:

- Objective disease progression according to RECIST 1.1 as determined by the investigator (patients who may derive clinical benefit may continue on treatment at the discretion of the investigator);
- Global deterioration of health status requiring discontinuation;
- Adverse event;
- Significant protocol violation;
- Lost to follow-up;
- Refusal for further treatment;
- Study termination by Sponsor;
- Pregnancy;
- Death.

Reasons for discontinuation from study follow-up may include:

- Study terminated by Sponsor;
- Lost to follow-up;
- Refusal for further follow-up for survival;
- Death.

If a patient does not return for a scheduled visit, every effort should be made to contact the patient. At least 2 attempts should be made to contact the patient, and each attempt should be recorded in the source documents. In any circumstance, every effort should be made to document patient outcome, if possible. The investigator should inquire about the reason for withdrawal, request that the patient returns for a final visit, and if applicable, follow-up with the patient regarding any unresolved adverse events.

If the patient withdraws from the study treatment and also withdraws consent for disclosure of future information, no further evaluations should be performed, and no additional data should be collected. The Sponsor may retain and continue to use any data collected before such refusal for further follow-up.

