Using the parameters identified, the ultimate sample size for each treatment arm is as many as 45 patients in the mITT population. The stopping rules (rejection regions), expressed as number of responses per patients treated, are 0/10, 1/14, 2/18, 3/22, 4/26, 5/29, 6/32, 7/35, 8/37, 9/39, 10/41, 11/43, 12/44, and 13/45. Thus, if more than 13 responses are observed among the first 45 patients enrolled who meet the criteria for the mITT population, the drug will be declared efficacious. If the true ORR is 20% (null hypothesis), the probability of early termination (under H_0) during the study is 0.92 and the expected sample size prior to termination is 28 patients. The Type 1 error is equal to 0.0499 and Power equal to 0.9065. If the true ORR is 40%, the probability of rejecting the hypothesis at each evaluation of the stopping rules varies, but cumulatively is 0.0935. If the true ORR is 40% and $N=45$, the exact 95% confidence interval (Clopper-Pearson) around the point estimate for ORR will be (25.7, 55.7). If the outcome in a treatment arm is promising and the option is taken to enroll up to 100 patients in the mITT in a specific treatment arm (45 patients in the initial arm plus 55 patients), to narrow the confidence interval around the ORR point estimate and to increase the size of the safety database, the exact 95% confidence interval around a true ORR of 40% will be (30.3, 50.3). Data collected in patients enrolled beyond the planned Phase 2 sample size will be used in secondary and supportive analyses. The primary analysis includes independent

evaluation of each of the four treatment arms in the first 45 patients; study expansion enables confirmation of the results of the primary analysis. The use of the Bayesian Predictive Probability Design within each arm effectively controls the overall Type I error to a maximum of 5% for each population of interest.

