Potential exists for individual tumor lesions to develop necrosis, to cavitate, have a flair response to treatment or become otherwise difficult to evaluate for a period of time as the result of beneficial study treatment impact. For example, tumor necrosis, cavitation or flair may result in increase in overall size of individual lesions or unclear tumor margins prior to recovery to smaller lesions, development of scar tissue, or complete resolution. The true tumor measurements of lesions should be recorded but the conclusion of progressive disease may be suspended until continued assessment clarifies the nature of the tumor change. If repeat assessments indicate progression of disease, then PD should be recorded on the date of the first assessment giving the impression of progression. If repeat assessments indicate that the change was a process of transition, then NE (not evaluable) should be recorded during the period of transition, and PR or CR may be recorded for subsequent evaluations. The CRF will collect information on the observations during the period of transition to support the assessment conclusions.

Supplemental Investigations

If CR determination depends on a residual lesion that decreased in size but did not disappear completely, it is recommended the residual lesion be investigated with biopsy or fine needle aspirate. If no disease is identified, objective status is CR.

Best Objective Response

Target Lesions	Non-Target Lesions	New Lesion	Point in Time Response	Best Response
CR	CR	No	CR	CR and PR require confirmation at least 4 weeks after first observation
CR	Non-CR/Non-PD	No	PR	
PR	Non-PD	No	PR	
SD	Non-PD	No	SD	SD requires an on-study assessment after at least 6weeks on treatment. Unconfirmed PR or CR are reported as SD.
PD	Any	Yes or No	PD	
Any	PD	Yes or No	PD	
Any	Any	Yes	PD	

Subjective Progression

Patients requiring discontinuation of treatment due to worsening health status attributable to advancement of the malignancy under study but without objective evidence of disease progression should not be reported as PD on tumor assessment CRFs. This should be indicated on the end of treatment CRF as off treatment due to Global Deterioration of Health Status.

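### Section 9.9 has no denominator category for a non-responder with recorded progression who stays on treatment, so a futility stop can come slightly late

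*Combined protocol and SAP*

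**What the plan says.** Section 9.9 bases the enrolment stopping rules on investigator assessments and lists who is counted. Item 2 puts three groups in the denominator. Group (a) is everyone who counts as a responder. Group (b) is anyone no longer taking study drug ("Patients discontinued from treatment"). Group (c) is defined by assessment: "Patients at the second or subsequent on-study disease assessment (scheduled after 4 treatment cycles, at Week 13) without PR, CR or PD", which the text then restricts to SD or NE. Item 3 keeps out patients on treatment who have not reached the first assessment, and "Patients on treatment with SD or NE at the first on-study disease assessment". Each patient's contribution is refreshed with the latest data at every evaluation.

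On treatment after progression, Section 3 says: "Study treatment will continue until disease progression, unacceptable adverse events, patient refusal or death". Section 6.5 lists objective progression among the criteria that may be used to stop study medication, but adds that "patients who may derive clinical benefit may continue on treatment at the discretion of the investigator". Under Appendix 2, when a change may be transient, "the conclusion of progressive disease may be suspended until continued assessment clarifies the nature of the tumor change".

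Two broader statements bear on the denominator. The Study Summary defines the mITT as all dosed patients, "For the purpose of making decisions for continued enrollment and for conduct of the final analysis for the Phase 2". Section 9.1 gives the boundaries as "expressed as number of responses per patients treated".

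**The concern.** A progressor without a response is a settled failure for ORR and should count against the drug as soon as PD is recorded. Item 2(c) removes PD by name, presumably because progressors are expected to arrive through 2(b) when they stop treatment. For a patient kept on treatment under Section 6.5, that route stays closed until treatment ends.

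A second route leads to the same gap. A patient counted under 2(c) with SD at Week 13 who later has PD on treatment no longer meets 2(c) and could drop out of the denominator when counts are refreshed.

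In both cases the counted response rate is too high for a time. At stake is how promptly the IDMC closes an arm that does not work, and so how many more patients enter it.

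**Working it through.** **1. The plan's own figures.** Inputs from Section 9.1: p0 = 0.20, p1 = 0.40, and boundaries 0/10, 1/14, 2/18, 3/22, 4/26, 5/29, 6/32, 7/35, 8/37, 9/39, 10/41, 11/43, 12/44, 13/45. Let f(n,k) be the probability that the arm is still open with k responses in n counted patients. Then f(n,k) = (1−p)·f(n−1,k) + p·f(n−1,k−1), and at each boundary all k at or below the limit are removed.

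| Quantity | Stated | Recomputed |
|---|---|---|
| P(stop before 45), p = 0.20 | 0.92 | 0.9199 |
| Expected N, p = 0.20 | 28 | 28.26 |
| Type I error | 0.0499 | 0.0499 |
| Power, p = 0.40 | 0.9065 | 0.9065 |

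All reproduce, with N read as patients whose outcome is counted.

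**2. Patient states set against Section 9.9.**

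| State | Place in 9.9 |
|---|---|
| Response | 2(a) |
| Off treatment, any reason | 2(b) |
| On treatment, SD/NE at second or later assessment | 2(c) |
| On treatment, before first assessment | 3(a), out |
| On treatment, SD/NE at first assessment | 3(b), out |
| On treatment, recorded PD, no response | none |

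PD suspended under Appendix 2 is not in the last row. It is not yet recorded as PD, and if the change proves transient the record is NE.

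**3. Effect at a boundary.** With 3 responses among 22 counted patients, 3 ≤ 3 and the arm stops. Leave one progressor out and the count is 3/21. The limit in force at 21 is 2 (from 2/18), so the arm continues. The limit at n−1 is one response lower than at n for every interim boundary after the first. For 0/10, nine counted patients fall short of the first look. So one uncounted patient reverses the decision at all 13 interim boundaries.

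**4. One look in isolation.** Take 22 known outcomes at p = 0.20. If all are counted, P(X ≤ 3) = 0.332. If 1 to 4 progressors (an assumed number) are uncounted, the denominator is 18 to 21, the limit is 2, and P(X ≤ 2) = 0.154. This shows local sensitivity only. Under continuous monitoring 0.1074 + 0.1100 + 0.0957 = 0.313 of null arms have already stopped at 10, 14 or 18.

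**5. Whole rule, simulated at ORR 20%.** The documents give no accrual rate, PD timing or share kept on treatment. Assumed: PD in 35% of non-responders at the first assessment and 35% of the rest at the second; responses first seen 65/25/10% at Weeks 6/12/18; progressors kept on stay 12 more weeks; a look after every change in count; 10,000 runs per cell. Reversal of unconfirmed responses is not modelled.

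| Accrual per month per arm | Mean enrolled at stop, none kept on | 10% kept on | 25% kept on | Added by gap (10%; 25%) |
|---|---|---|---|---|
| 0.5 | 29.3 | 29.5 | 29.7 | 0.2; 0.4 |
| 1 | 30.3 | 30.6 | 31.0 | 0.3; 0.7 |
| 2 | 32.2 | 32.7 | 33.4 | 0.5; 1.2 |
| 4 | 35.7 | 36.5 | 37.6 | 0.8; 1.9 |

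The probability of crossing a boundary before 45 are counted stays at 0.91 to 0.93 in every cell. At ORR 40% the gap does not raise futility stops (0.05 to 0.07 throughout).

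A separate stress run kept 60% of progressors on for 24 weeks, with slightly different timing assumptions and 4,000 runs per cell. Mean enrolled rose from 29.4, 30.2, 32.2 and 35.3 to 31.1, 33.4, 37.5 and 42.2 at the same four rates, so the gap added 1.7, 3.2, 5.3 and 6.9 patients.

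**6. Final test.** With no futility stop at all, P(X ≥ 14 | 45, 0.20) = 0.0521, against the stated 0.0499. That is the ceiling on any effect of missed stops on Type I error.

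**The case against.** The strongest reply is that the plan as a whole already counts these patients. The mITT for enrolment decisions is every dosed patient, the boundaries are per patient treated, item 3 does not exclude on-treatment progressors, and Section 9.9 calls its items guidelines. Most progressors will leave treatment and enter through 2(b), suspected transient progression is outside the gap, and the IDMC charter may deal with the case.

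Much of this stands, and it is why the effect is small and usually temporary. It does not close the gap. Section 9.9 deliberately departs from counting all dosed patients, and 2(c) takes PD out by name, so someone applying the list has no instruction for this patient. The charter is not among the documents.

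A reader might infer three stronger points, which the documents do not support:

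- *That the expected 28 is wrong or clashes with Section 9.9.* It reproduces in counted patients. More will be enrolled than counted at the stop, but Section 3 says enrolment is not paused and makes the IDMC responsible for limiting over-enrolment, so the difference is acknowledged. Section 9.1 does not call 28 the number enrolled.
- *That Section 9.1 has the 0/10 boundary judged on ten first scans.* It says when monitoring opens. Section 9.9 defines the denominator and holds back on-treatment SD/NE patients at the first assessment. Read together, 0/10 applies once ten patients are counted.
- *That the gap could produce a false efficacy claim.* The primary analysis uses centrally reviewed confirmed responses in the mITT, which includes every dosed patient, and the ceiling in step 6 is 0.0521.

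**Conclusion.** The concern holds as a minor fault in the counting rule. Read as written, Section 9.9 leaves a non-responder with recorded PD on treatment out of the denominator until treatment stops, and may drop one already counted as SD. This delays a futility stop in an ineffective arm. The reversal at the boundaries follows from the documents alone. The delay in patients does not: it rests on assumed accrual, timing of progression and share kept on treatment. At 10% kept on for 12 weeks it is about 0.2 to 0.8 patients per arm, and it grows to several patients only if most progressors stay on for months. The stated operating characteristics are correct and the primary analysis is untouched.

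**What to change.** Add to Section 9.9 item 2: *d. Patients with investigator-recorded PD and no qualifying response, once PD is recorded in the CRF, whether or not treatment continues.* State that PD suspended under Appendix 2 is not counted until it is recorded. Align the IDMC charter if it does not already say this. With every such patient counted, the figures in step 1 again describe the rule as applied to counted patients.

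Optionally, add a cross-reference in Section 9.1 saying that the 0/10 boundary and the expected 28 refer to patients counted under Section 9.9.

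The wording on treatment at progression in Sections 3 and 6.5 should be reconciled by those responsible for it. The line above works either way and takes no position on treatment after progression.

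The cost is a short protocol amendment or administrative letter, which under Section 13.1 needs IRB/EC approval before use. The added line removes only the delay from uncounted progressors. The lag from SD/NE patients waiting for the second assessment remains, as the plan intends.

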10 ETHICS AND RESPONSIBILITIES

10.1 Ethical Conduct of the Study

This study will be conducted in accordance with International Ethical Guidelines for Biomedical Research Involving Human Patients (Council for International Organizations of Medical Sciences 2002), Guidelines for Good Clinical Practice (GCP) (International Conference on Harmonization [ICH] 1996), and concepts that have their origin in the Declaration of Helsinki (World Medical Association 1996, 2008 & 2013). Specifically, this study is based on adequately performed laboratory and animal experimentation; the study will be conducted under a protocol reviewed and approved by an IRB/EC; the study will be conducted by scientifically and medically qualified persons; the benefits of the study are in proportion to the risks; the rights and welfare of the patients will be respected; the physicians conducting the study do not find the hazards to outweigh the potential benefits; and each patient will give his or her written informed consent before any protocol-driven tests or evaluations are performed.

